# Table 1. Clinical Measures Enacted Upon Increasing Severity ofECHO Findings

	Valve			
Severity	Aortic	Mitral	Pulmonary	Tricuspid
Trace (≤18 years)	Level 2	Level 2	Level 1	Level 1
Trace (>18 years)	Level 1	Level 1	Level 1	Level 1
Mild (≤18 years)	Level 2	Level 2	Level 1	Level 1
Mild (>18 years)	Level 2	Level 1	Level 1	Level 1
Moderate	Level 3	Level 3	Level 3	Level 3
Severe	Level 3	Level 3	Level 3	Level 3

Level 1: Continue per protocol

Level 2:

- 1. If there is a desire to continue study medication:
  - a. The principal investigator will evaluate the efficacy to date based on study diaries and consult with the parent/guardian, and determine whether study treatment was associated with significant, meaningful benefit in number, severity and/or duration of seizures and/or on the impact on daily functioning.
  - b. The principal investigator will consider whether the subject has had reasonable trials (dose and duration) of other available anticonvulsants, alone or in combination, and not maintained the level of seizure control currently achieved with study medication.
- 2. If the principal investigator feels consideration of continued treatment is warranted considering benefit and potential risk, and the parent/guardian feels strongly that the child be maintained on the study medication when understanding the risks, the parent/guardian must sign a statement acknowledging their understanding of the positive findings and possible risks associated with continuing in the study. The child should provide assent if appropriate. If both of these conditions are not met, the subject is discontinued from treatment.
- 3. The principal investigator prepares a case history and rationale for continuation to review with the local cardiologist, including consideration of effects on seizures and comorbidities.
- 4. The principal investigator and local cardiologist will make a determination of appropriate path, including the possible outcomes:
  - a. Discontinue study medication
  - b. Increase frequency of ECHO and ECG monitoring
  - c. Add additional ECG and/or ECHO measures to be monitored
  - d. Reduce the dose of study medication

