# **IV. SUBJECT ENROLLMENT**

This site will independently be studying the efficacy of ZX008 on seizure frequency in children and young adults with Sunflower Syndrome and the effects of ZX008 on EEG patterns and quality of life.

Informed consent will be obtained for each subject who participates in the study by the LPI and be documented in writing with the PHRC approved consent form. The LPI and/or the research nurse will initially explain the study, provide the informed consent form, and answer any questions from the subjects and their family members. Subjects will be given adequate time to make their decision. Subjects will have the opportunity to take the consent form home, and call back if they wish to participate. Subjects will also be encouraged to discuss any concerns they have with other health care providers. Informed consent for all subjects will be obtained by [name]., Ph.D.. The potential for coercion will be avoided through ensuring the subject that participation in the study is completely voluntary, and that deciding not to take part in the study will not affect the care or benefits to which the subject is otherwise entitled. Subjects will be enrolled in the study once informed consent has been obtained. Only the LPI will be obtain consent from the subject, the subject's parent/quardian or the subject's surrogate

For subjects who are older than 18 years of age with impaired decision making, and subjects under 18 years of age, legal consent to participate in research will be provided by a parent or an individual authorized under applicable state or local law to provide consent on the subject's behalf to general medical care. When enrolling a subject who is younger than 18 it is sufficient for consent to be obtained from just one parent. Before the LPI allows an individual other than a parent to consent on behalf of a child, she will document the basis for the individual's authority to consent on behalf of the child to general medical care and place any relevant documentation in the research file.

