In addition to permission of the parent(s) or guardian, assent to participate in the study must be obtained from each child age 7 to 17 years old who, in the opinion of the LPI, is able to provide assent based on their age, maturity or psychological state. When obtained, assent for subjects 14 through 17 years of age will be documented using the PHRC approved Consent Form and assent for subjects 7 through 13 years of age will be documented in writing using the PHRC approved Assent Form. When assent is not obtained, the LPI will document the rationale in the research records.

The following categories of surrogates (listed in general order of preference) may provide consent in writing on behalf of potential subjects incapable of providing informed consent:

- 1. Court appointed guardian with specific authority to consent to participation in research or authority to make health care decisions for a class of diagnostic and therapeutic decisions inclusive of the proposed research;
- 2. Health care proxy/person with durable power of attorney with specific authority for making health care decisions inclusive of the proposed research; or
- 3. Spouse, adult child, or other close family member who knows the subject well and has been involved in their care.

Assent of subjects will be a requirement for participation in the research unless the subject is incapable of giving assent due to his/her medical condition. If the individual objects to participation, s/he will not be enrolled. When surrogate consent is relied upon, the LPI will ensure that the surrogate understands that his or her decisions should be based on "substituted judgment." This means that the decision reflects a potential subject's own views when s/he had the capacity to express them. The PHRC preferred order of surrogates will be followed,

and the Investigator will document the relationship of the surrogate to the subject in the research record.

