#### Thickening of Heart Valves; Pulmonary Hypertension:

When the active ingredient in ZX008, fenfluramine, was on the market for the treatment of obesity in adults who were overweight from the 1970s through the 1990s, some adults developed thickening of heart valves and pulmonary hypertension (high pressure in blood vessels in the lung that makes it difficult to breathe normally). After stopping the medication, some patients' heart valves returned to normal, some remained stable but abnormal, and some had surgery to correct the condition. Generally, if these problems do occur, they develop slowly over time. The subject will be administered ECHOs during the study to very carefully watch for early signs that the subject's heart valves are thickening and to look for early signs of pulmonary hypertension. If there are heart valve changes, the subject will re-review the risk and potential benefit of the study medication with the study doctor and discuss further options. The subject may withdraw at this or any other time. If the subject experiences any chest pain, persistent cough, shortness of breath, wheezing, extreme fatigue, or dizziness, they should contact the study staff immediately to discuss whether they should have a clinic visit or other tests.

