#### Level 3:

1. The principal investigator will evaluate efficacy to date based on study diaries and consult with the parent/guardian, and determine whether the achieved benefit justifies the consideration of continuing study treatment. MINIMAL efficacy criteria for consideration:

- a. Seizures must be more than 75% improved (number of convulsive seizures per 28 days) on treatment over baseline, and improvement must be consistent.
- b. The number, type, duration, and distribution of seizures at baseline should be of a severity, which justifies the risks of cardiopulmonary complications, considering the subject's age and overall health.
- c. Subject has had reasonable trials (dose and duration) of other available anticonvulsants, alone or in combination, and not maintained the level of seizure control achieved with study medication.
- 2. If the principal investigator feels consideration of continued treatment is warranted considering benefit and potential risk, and the parent/guardian feels strongly that the child be maintained on the study medication when understanding the risks, the parent/guardian must sign a statement acknowledging their understanding of the positive findings and possible risks associated with continuing in the study. The child should provide assent if appropriate. If both of these conditions are not met, the subject is discontinued from treatment.
- 3. The principal investigator prepares a case history and rationale for continuation to review with the local cardiologist, including consideration of effects on seizures and comorbidities.
- 4. The principal investigator and local cardiologist will evaluate the risks and proposed monitoring plan, if applicable.
- 5. The principal investigator and local cardiologist will make a determination of appropriate path, including these possible outcomes:
  - a. Discontinue study medication
  - b. Increase frequency of ECHO and ECG monitoring
  - c. Add additional ECG and/or ECHO measures to be monitored
  - d. Reduce the dose of study medication

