In addition to reporting adverse events to the Partner's IRB, the LPI will also report them to the FDA in the form of a written IND safety report. The IND safety report will be submitted on form 3500A and accompanied by form 1571.

The LPI will also monitor the adherence to the protocol and to Good Clinical Practice, the progress of enrollment, and make sure that study drug is being stored, dispensed, and accounted for according to specifications. The subjects will be closely monitored for side effects during the treatment period.

Parents/subjects are instructed how to administer the study drug at each study visit.

The subject will be withdrawn from the treatment for any of the following reasons:

- 1. Development of signs or symptoms indicative of cardiac valvulopathy or regurgitation (mitral, aortic, tricuspid, pulmonary valves), or pulmonary hypertension for which the local cardiologist and the investigator believe the benefit of continued participation does not outweigh the risk.
- 2. Subject is noncompliant with procedures set forth in the protocol in an ongoing or repeated manner.
- 3. Subject experiences an AE or SAE that warrants withdrawal from the treatment.
- 4. Clinically significant worsening of seizures, judged by investigator or caregiver such that treatment outside of the protocol and treatments other than ZX008 are assumed to be in the subject's best interest. Frequent or increased use of rescue medication may be considered indicative of worsening seizures.
- 5. It is the investigator's opinion that it is not in the subject's best interest to continue in the treatment.

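### After a valve finding, Levels 2 and 3 let only a parent or guardian ask for and sign off continued treatment, yet Table 1 applies these levels to capable adults.

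*Protocol*

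**What the plan says.** Section VII grades echocardiogram findings by valve and severity in Table 1 and assigns each a level of oversight when the result has progressed. The trace and mild rows are split by age at 18. The row beginning "Mild (>18 years" puts an aortic finding at Level 2. The moderate and severe rows have no age split and are Level 3 for all four valves.

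Item 2 is worded identically in Levels 2 and 3. Besides the investigator's view that continuing may be warranted, the parent or guardian must feel strongly that the child should stay on the drug, and "the parent/guardian must sign a statement acknowledging their understanding of the positive findings and possible risks associated with continuing in the study". For the patient it says: "The child should provide assent if appropriate". It ends: "If both of these conditions are not met, the subject is discontinued from treatment". Item 1 of each level also names only the parent or guardian as the person the investigator consults.

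Section IV deals with who consents. Its rule for consent by a parent or other authorised person opens "For subjects who are older than 18 years of age with impaired decision making, and subjects under 18 years of age, legal consent". Its list of surrogates is of people who "may provide consent in writing on behalf of potential subjects incapable of providing informed consent". Documented assent is described for ages 7 to 17.

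**The concern.** The inclusion criteria admit patients aged 4 to 25, and Table 1 has rows made for those over 18. The table therefore recognises adults, but the procedure it triggers is written for a child with a guardian. A capable adult has no stated part in item 2, either as the person who wants to continue or as the person who signs.

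At stake is the signed risk acknowledgement for staying on the drug after progression of valve disease, the harm this protocol monitors most closely. Two wrong outcomes are possible on the text. A capable adult who is benefiting could be discontinued because a parent is unavailable or unwilling to sign. Or an adult could continue with a parent's signature on file and no required record of the adult's own agreement.

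**Working it through.** There is no figure in the plan to reproduce. The check has two parts: whether Table 1 really leads adults to item 2, and whether anything else in the protocol gives them another route.

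**Counting Table 1.** Four valves by four severities give 16 cells for each age group.

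| Severity | Over 18: Level 2 | Over 18: Level 3 | 18 or under: Level 2 | 18 or under: Level 3 |
|---|---|---|---|---|
| Trace | 0 | 0 | 2 (aortic, mitral) | 0 |
| Mild | 1 (aortic) | 0 | 2 (aortic, mitral) | 0 |
| Moderate | 0 | 4 | 0 | 4 |
| Severe | 0 | 4 | 0 | 4 |
| Total | 1 | 8 | 4 | 8 |

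- Over 18: 1 + 8 = 9 of 16 cells lead to item 2.
- 18 or under: 4 + 8 = 12 of 16. A patient aged exactly 18 is in this group, although documented assent under section IV stops at 17.

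**Setting the sections side by side.**

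1. *Section III* admits patients to age 25. Section V continues visits every 6 months after Visit 5 for responders, so a patient who enters as a minor can also turn 18 on treatment.
2. *Section IV* gives the decision to a parent or authorised person for minors and for adults with impaired decision making, and limits surrogates to subjects who cannot consent. It also lists the subject among those from whom consent is obtained. It never says in one sentence that capable adults consent for themselves, but no other reading is coherent.
3. *Section VII, on heart-valve thickening*, says that after valve changes "the subject will re-review the risk and potential benefit of the study medication with the study doctor and discuss further options", and that the subject may withdraw at any time. This gives the adult a discussion and a way out. It requires no signed acknowledgement from the adult and does not lift the parent or guardian condition.
4. *Section IX, withdrawal criterion 1*, covers valve disease "for which the local cardiologist and the investigator believe the benefit of continued participation does not outweigh the risk". This is a clinical benefit-risk judgement. It does not replace the separate discontinuation rule in item 2, nor say who signs for an adult.

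No section supplies an adult route through Levels 2 and 3.

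**The case against.** The strongest reply is that item 2 is plainly about a child with a guardian, so a sensible site would apply it to minors only and let adults sign for themselves. On that view the protocol is silent about adults and imposes no wrong rule on them. It can be added that the signature acknowledges risk and is not research consent, that section IV stays in force, and that the investigator and local cardiologist decide the outcome. A capable adult can withdraw at any time and cannot be kept on the drug unwillingly. A caregiver is expected for every subject, so a parent will often be at hand. The acknowledgement form is not shown and may have a line for an adult.

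Much of this stands, and it limits the practical harm. For an adult who continues, what is missing is a required written record, not the freedom to refuse. A required caregiver need not be a parent or guardian, however, so that point does not remove the risk of an adult being stopped for want of a signature.

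The minors-only reading does not rescue the text. Item 2 does not limit itself to minors, Table 1 expressly sends adults to it, and if it is read as limited, adults at Levels 2 and 3 have no acknowledgement procedure at all. Either reading leaves something to correct.

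**Conclusion.** The concern holds. Item 2 of Levels 2 and 3 is wrong as written for capable adults: it makes continuation depend on the wish and signature of a person who, under section IV, does not decide for them.

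The rule is reached from 9 of 16 cells of Table 1 for patients over 18 and from 12 of 16 at exactly 18. How many patients this means cannot be derived from the protocol, and it may be very few or none. Up to 20 patients are followed, they come from a pediatric clinic, valvulopathy is excluded at entry, and the levels apply only on progression.

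Two assumptions are made: that capable adults consent for themselves, inferred from section IV, and that adulthood begins at 18. The contents of the acknowledgement form could not be checked. No endpoint or analysis is affected. The point concerns protection of participants and consistency of the protocol, and it should be corrected, but it does not threaten the trial's conclusions.

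**What to change.** In items 1 and 2 of Levels 2 and 3, replace the parent or guardian and the child with wording to this effect: the subject, if 18 or older and with capacity; otherwise the parent, guardian or surrogate, with the subject's assent where appropriate. Make the same change on the acknowledgement form and check that it has a signature line for an adult subject.

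The efficacy thresholds, the review with the local cardiologist and the possible outcomes stay as they are. The cost is a wording amendment to the protocol and the form, with no added procedures, visits or data.

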#### Level 3:

1. The principal investigator will evaluate efficacy to date based on study diaries and consult with the parent/guardian, and determine whether the achieved benefit justifies the consideration of continuing study treatment. MINIMAL efficacy criteria for consideration:

- a. Seizures must be more than 75% improved (number of convulsive seizures per 28 days) on treatment over baseline, and improvement must be consistent.
- b. The number, type, duration, and distribution of seizures at baseline should be of a severity, which justifies the risks of cardiopulmonary complications, considering the subject's age and overall health.
- c. Subject has had reasonable trials (dose and duration) of other available anticonvulsants, alone or in combination, and not maintained the level of seizure control achieved with study medication.
- 2. If the principal investigator feels consideration of continued treatment is warranted considering benefit and potential risk, and the parent/guardian feels strongly that the child be maintained on the study medication when understanding the risks, the parent/guardian must sign a statement acknowledging their understanding of the positive findings and possible risks associated with continuing in the study. The child should provide assent if appropriate. If both of these conditions are not met, the subject is discontinued from treatment.
- 3. The principal investigator prepares a case history and rationale for continuation to review with the local cardiologist, including consideration of effects on seizures and comorbidities.
- 4. The principal investigator and local cardiologist will evaluate the risks and proposed monitoring plan, if applicable.
- 5. The principal investigator and local cardiologist will make a determination of appropriate path, including these possible outcomes:
  - a. Discontinue study medication
  - b. Increase frequency of ECHO and ECG monitoring
  - c. Add additional ECG and/or ECHO measures to be monitored
  - d. Reduce the dose of study medication

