# I. BACKGROUND AND SIGNIFICANCE

Drug resistant epilepsy is a serious and potentially life-threatening condition that impacts the day to day functioning of those affected. Patients with drug resistant epilepsy are at a higher risk for Sudden Unexpected Death in Epilepsy (SUDEP), as frequency of generalized tonic-clonic seizures, poly therapy, number of anti-epileptic drugs (AED) used, and propensity for nocturnal seizures are the leading risk factors for SUDEP. Annual SUDEP risk for patients with epilepsy is 1/1000; whereas SUDEP risk for patients with drug resistant epilepsy is 1/150.

Patients with drug resistant epilepsy do not respond or respond incompletely to FDA approved AEDs. Children living with drug resistant epilepsy are particularly vulnerable, and urgently need more effective medications because those suffering from early-onset and high seizure burden epilepsies suffer the greatest neurodevelopmental problems, including intellectual disability and autism. In some syndromes such as Dravet Syndrome, recent evidence suggests that more effective early control of epilepsy is associated with better developmental outcomes than in children who were treated 20-30 years ago (Chieffo et al., 2011).

Sunflower Syndrome (also referred to as Self-induced Photosensitive Epilepsy) is a rare epileptic disorder characterized by a distinctive seizure that manifests itself in a highly stereotyped physical behavior. Seizure types associated with Sunflower Syndrome include absence seizures and generalized tonic-clonic seizures. Associated with these seizures, individuals with Sunflower Syndrome obsessively seek out a light source, stare at the light source, and wave one hand in front of their eye (Belcastro & Striano, 2014; Ames, 1971; Aicardi & Gastaut, 1985). Electroencephalogram (EEG) features include generalized spike and wave discharges interictally, and typically a strong photoparoxysmal response during photic stimulation (Belcastro & Striano, 2014; Ames & Saffer,

Detailed Protocol Version Date 02/21/2020 1

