The primary efficacy measure was a comparison of the change in mean monthly convulsive seizure frequency between ZX008 0.8 mg/kg/day and placebo during the 14-week treatment period compared with the 6-week baseline observation period. Subjects taking ZX008 0.8 mg/kg/day achieved a 63.9% reduction in mean monthly convulsive seizures compared to placebo (p<0.001). The median percent reduction in monthly convulsive seizure frequency was 72.4% among ZX008 0.8 mg/kg/day subjects compared to 17.4% in placebo subjects.

A key secondary endpoint was the same analysis for a comparison of ZX008 0.2 mg/kg/day and placebo. Subjects taking ZX008 0.2 mg/kg/day achieved a reduction in mean monthly convulsive seizures of 33.7% compared to placebo (p=0.019). Collectively, these top-line data suggest a dose-response relationship for ZX008 in the adjunctive treatment of convulsive seizures in Dravet syndrome" ("Zogenix Announces Positive Top-line Results from Pivotal Phase 3 Clinical Trial of ZX008 in Dravet Syndrome", September 2017).

There are no treatments specifically approved for the treatment of Sunflower Syndrome in the United States. Broad spectrum anticonvulsant medications, including sodium valproate, lamotrigine, levetiracetam, and clobazam, have not shown full efficacy in seizure prevention in patients with Sunflower Syndrome. Accordingly, there remains a significant unmet need for an approved treatment for children and adults with Sunflower Syndrome.

As this epilepsy typically does not respond to anticonvulsant medications, and since Aicardi described the successful treatment with fenfluramine of at least one child with this syndrome, we would like to investigate if fenfluramine is an effective, safe and well tolerated treatment for Sunflower Syndrome.

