# **II. SPECIFIC AIMS**

The primary objective of this study is the determine the efficacy of ZX008 on seizure frequency in children and young adults with Sunflower Syndrome. The goal of treatment is to provide a 30 percent or greater reduction of generalized tonic-clonic seizures and/or hand waving associated with absence seizures.

Secondary objectives of the study include evaluation of the effect of ZX008 (fenfluramine hydrochloride) on EEG patterns and quality of life. Patients with Sunflower Syndrome often experience low self-esteem, bullying due to the unusual motor movements associated with their seizures, school performance issues, anxiety, and depression.

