# The inclusion criteria for enrollment in this study include:

- Subject is male or non-pregnant, non-lactating female, age 4 to 25 years, inclusive as of the day of the screening visit. Female subjects of childbearing potential must have a negative serum pregnancy test at screening. Subjects of childbearing or child-fathering potential must be willing to use medically acceptable forms of birth control, which includes abstinence, while in this study and for 90 days after the last dose of study drug.
- Subjects must have a diagnosis of Sunflower Syndrome, where seizures are not completely controlled by their current treatment plan.

- Subjects must experience seizures including absence seizures and/or generalized tonic-clonic seizures which involve seeking out a light source, staring at the light source, and waving one hand in front of their eye(s). Subject's must experience an average of 6 handwaving associated with absence seizures and/or generalized tonic-clonic seizures per week.
- Evidence of EEG in the medical history that shows generalized spike and wave discharges between seizures and a strong photoparoxysmal response during photic stimulation. Acceptable evidence includes a copy of the EEG trace, EEG report, or physician note that appropriately describes the EEG findings.
- All medications or interventions for epilepsy must be stable for at least 4 weeks prior to screening and are expected to remain stable until Month 3.
- Subject and/or parent/guardian has been informed of the nature of the study and informed consent has been obtained from the subject and/or legally responsible parent/guardian.
- Subject has provided assent in accordance with Institutional Review Board (IRB)/Ethics Committee requirements, if capable.
- Subjects parent/caregiver is willing and able to be compliant with diary completion, visit schedule, and study drug accountability.

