# **V. STUDY PROCEDURES**

The investigational drug to be used in this study is fenfluramine hydrochloride (ZX008) manufactured by Zogenix, Inc..

ZX008 will be supplied as an oral solution in a concentration of 2.5 mg/mL. The subjects will be treated on an outpatient basis and will not require hospital admission. ZX008 will be administered on a twice daily basis.

The study will initially consist of a 4 week baseline period, during which handwaving associated with absence seizures and/or generalized tonic-clonic seizures will be recorded in a seizure diary on a daily basis. Subjects will meet enrollment criteria if they have an average of 6 generalized tonic-clonic and/or handwaving associated absence seizure per week.

If enrollment criteria is met, the subject will enter a titration period. The starting dose will be 0.2 mg/kg/day for the first 14 days. The dose will be increased every 2 weeks as tolerated by 0.2 mg/kg/day, to a maximum dose of 0.8 mg/kg/day, or a total maximum dose of 30 mg/day. The subject will remain on 0.8 mg/kg/day, 30 mg/day, or maximum tolerated dose for a 6 week maintenance period.

Site personnel will call the subject and/or their parent/caregiver every 11-14 days during the titration period before their next scheduled dose increase.

There will be 5 study visits within a 6 month period. After Visit 5, visits will occur every 6 months for an assessment in the clinic for subjects who respond to treatment with at least a 30% reduction in seizure frequency.

Seizure frequency will be tracked with the use of a daily seizure log. In the event that seizure frequency is markedly reduced compared to baseline after starting the study drug the LPI will discuss with the subject and/or their caregiver about adjusting the dose of concomitant seizure medications. If seizure frequency is markedly increased compared to baseline after discontinuing other medications which were taken as standard of care the LPI may decide to adjust dose of other seizure medications or reintroduce the medications that were taken as

IND Visit Schedule					
Visit Number	Visit Type	Time Point			
1	Baseline	Day -28			
2	Titration	Day 1 (+14 days)			
3	Titration and/or	28 days from Visit 2			
	Maintenance	(±7 days)			
4	Maintenance	56 days from Visit 2			
		(±14 days)			
5	Maintenance	84 days from Visit 2			
		(±14 days)			
Continuous	Maintenance	Each 6 Months			
		following Visit 5			
		(±14 days)			

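### Level 3 criterion 1a counts convulsive seizures only, so it has no defined result for an eligible patient with no convulsive seizures at baseline

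*Protocol*

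**What the plan says.** Section VII, Level 3 applies to moderate or severe findings on any of the four valves (Table 1). Its item 1 introduces "MINIMAL efficacy criteria for consideration", and criterion 1a reads: "Seizures must be more than 75% improved (number of convulsive seizures per 28 days) on treatment over baseline, and improvement must be consistent".

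The study's other rules use a different count:

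- Section II sets the goal as a "30 percent or greater reduction of generalized tonic-clonic seizures and/or hand waving associated with absence seizures".
- The inclusion criteria in Section III say that subjects "must experience an average of 6 handwaving associated with absence seizures and/or generalized tonic-clonic seizures per week".
- Section V repeats this for the 4-week baseline: "Subjects will meet enrollment criteria if they have an average of 6 generalized tonic-clonic and/or handwaving associated absence seizure per week".
- Level 2 in Section VII asks about "significant, meaningful benefit in number, severity and/or duration of seizures and/or on the impact on daily functioning", with no restriction to convulsive seizures.

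Section I states: "Seizure types associated with Sunflower Syndrome include absence seizures and generalized tonic-clonic seizures". The protocol does not define convulsive. Apart from criterion 1a, it speaks of convulsive seizures only when describing the Dravet trial in Section I, whose primary measure was "a comparison of the change in mean monthly convulsive seizure frequency".

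**The concern.** Criterion 1a is a percentage change from baseline in one seizure type, and the protocol admits patients who need not have that type at all. For such a patient the baseline denominator is zero and the percentage does not exist. Criterion 1a is also the only numeric efficacy criterion at Level 3, so nothing else there gives a measured answer in its place. The same patient can be assessed on efficacy at Level 2.

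What is at stake is an individual decision on continued exposure after a serious valve finding. As the text stands, two investigators could apply 1a differently to identical diaries. A patient whose qualifying seizures have all stopped could be treated as failing the criterion, or as outside its scope, and the protocol supports neither reading explicitly.

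**Working it through.** The protocol gives no figure to reproduce here. The check applies criterion 1a to patients whom the entry criteria allow.

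**Inputs**
- Eligibility: an average of 6 qualifying seizures per week, of either type (Sections III and V).
- Baseline: 4 weeks (Section V), the same 28-day unit as in 1a.
- Threshold: improvement of more than 75% in convulsive seizures (Section VII, Level 3, 1a).
- Assumption: convulsive means generalized tonic-clonic, the only convulsive type among the two that Section I names for this syndrome.
- The seizure mixes below are illustrative; the protocol gives no distribution.

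**Formula.** Improvement = (B − T)/B, where B is the baseline count and T the on-treatment count, both per 28 days. Criterion 1a requires (B − T)/B > 0.75.

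**Baseline count.** 6 per week × 4 weeks = 24 qualifying seizures. All 24 may be hand-waving absences, so a convulsive B of 0 is allowed.

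**Case A, no convulsive seizures at baseline.** 24 absence and 0 tonic-clonic seizures fall to 0 and 0.
- Study's combined count: (24 − 0)/24 = 100%.
- Criterion 1a: (0 − 0)/0, undefined.

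**Case B, one convulsive seizure at baseline.** 23 absence and 1 tonic-clonic seizure fall to 0 and 1.
- Combined count: (24 − 1)/24 = 95.8%.
- Criterion 1a: (1 − 1)/1 = 0%, not met.

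**Small convulsive baselines.** The largest T that satisfies 1a:

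| Convulsive baseline B | Largest T with improvement above 75% |
|---|---|
| 0 | undefined |
| 1 to 4 | 0 |
| 5 to 8 | 1 |
| 24 | 5 |

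At B = 4, T = 1 gives exactly 75%, which is not more than 75%. With 1 to 4 baseline convulsive seizures, 1a therefore demands complete freedom from them.

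**Search for a rule that covers Case A.** Criterion 1b mentions seizure type but concerns baseline severity. Criterion 1c concerns trials of other anticonvulsants. Items 2 to 5 cover the signed acknowledgement, case history, cardiology review and possible outcomes. The withdrawal reasons in Section IX leave the cardiac benefit-risk judgement to the investigator and local cardiologist. None gives a result for 1a at a zero baseline.

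**The case against.** The strongest reply is that 1a is a hurdle to be cleared, not an endpoint to be analysed. A patient with no convulsive seizures at baseline cannot show the required improvement, so the hurdle is not cleared and the default falls away from continued exposure. Cardiac protection is then intact: valve grading and Level 3 oversight do not depend on 1a, and Section IX separately provides for withdrawal when benefit does not outweigh cardiac risk.

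A stricter, narrower test at Level 3 than at Level 2 is also coherent as graded oversight. Section I lists tonic-clonic seizure frequency among the leading risk factors for sudden death in epilepsy, so a convulsive-only test could be deliberate. Entry, goal and continuation rules need not share one seizure count. The situation also needs several uncommon things to coincide in a study of up to 20 patients.

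Much of this stands. The wording does lean towards not met, a deliberate choice is possible, and Case B alone shows only that two measures diverge, since 1a can be evaluated there. The difference from Level 2 is likewise no error in itself. But the protocol states neither the default nor the rationale, and a deliberate convulsive-only test would still leave the zero baseline unaddressed. If not met is the intended reading, absence-only patients fail 1a whatever their response, and that consequence should be written down rather than inferred.

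**Conclusion.** The point holds and should be fixed. Applied as written, criterion 1a gives 0/0 for a patient type that the protocol expressly admits, including one who is 100% improved on the study's own seizure count. At a low convulsive baseline it can be evaluated but can depart sharply from that count (0% against 95.8% in the illustration).

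This rests on reading convulsive as generalized tonic-clonic. If hand-waving events were meant to be included, the text does not say so and the sections still need reconciling.

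The reach is limited. Only absence-only or low-convulsive patients who also have a moderate or severe valve finding are affected; their number is not given and may be zero. The other Level 3 requirements still apply, and eligibility, the primary objective and the diary data are untouched.

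**What to change.** Reconcile Section VII, Level 3 with Sections II, III and V. State which seizure types criterion 1a counts, and how it applies when the baseline count of those seizures is zero. If the restriction to convulsive seizures is intended, say so and give the reason. The threshold and the clinical rule remain with the sponsor, the investigator and the cardiologist; nothing here argues for a particular one.

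The cost is one or two sentences in Section VII. No new data are needed, because the daily diary in Section V already records every seizure type with its frequency and duration. It is best settled before a Level 3 case arises.
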